6. DOSING DELAYS/DOSE MODIFICATIONS

6.1 Recommended Criteria for Beginning or Delaying a Subsequent Treatment Cycle

Patients must meet eligibility criteria on Cycle 1 Day 1 to begin treatment. There are no pre-treatment criteria to begin a new cycle of nivolumab.

For a new cycle of treatment with lenalidomide to begin, the patient must meet the following criteria:

- ANC must be $\geq 1,000/\mu\text{L}$.
- Platelet count must be $\geq 50,000/\mu\text{L}$.
- All other clinically significant, study drug related non hematologic toxicity must have resolved to \leq Grade 1 or to baseline condition

If the participant fails to meet the above-cited criteria for initiation of a new cycle of treatment on day 1 of the cycle, dosing of all medications should be delayed for 1 week. At the end of that time, the participant should be re-evaluated to determine whether the above criteria have been met. If the participant continues to fail to meet the above-cited criteria, delay therapy and continue to re-evaluate. The maximum delay for toxicity related to study treatment before treatment is permanently discontinued will be 3 weeks. If a delay of > 3 weeks is clinically necessary, and the patient is showing benefit from treatment, the patient may continue on study after discussion and approval by the Principal Investigator.

If any one of the study medications is permanently discontinued for any reason including toxicity, or FDA mandate, the patient may remain on the study at the discretion of the principal investigator.

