6.3 Lenalidomide

Hematologic Toxicities: For adverse hematologic events that are considered possibly, probably or definitely related to Lenalidomide, the following criteria for retreatment and dose modification should be followed unless discussed and approved first by the overall principal

CONFIDENTIAL

This document is confidential. Do not disclose or use except as authorized.

investigator. The treating investigator should determine the clinical significance of laboratory values and attribution to study medications before a treatment decision is made. All instances where lenalidomide is held, the dose will be considered missed, and will not be made up.

Non Hematologic Toxicity: For adverse non hematologic events that are considered to be possibly, probably or definitely related to Lenalidomide, the following criteria for retreatment and dose modification should be followed unless discussed and approved first by the overall principal investigator. The treating investigator should determine the clinical significance of laboratory values or radiographic findings and attribution to study medications before a treatment decision is made. All instances where lenalidomide is held, the dose will be considered missed, and will not be made up.

Dose delays and modifications should be made as indicated in the following table(s) unless first discussed with the Overall PI. The descriptions and grading scales found in the revised NCI Common Terminology Criteria for Adverse Events (CTCAE) version 4.0 will be utilized for dose delays and dose modifications. A copy of the CTCAE version 4.0 can be downloaded from the CTEP website

http://ctep.cancer.gov/protocolDevelopment/electronic_applications/ctc.htm.

Table 12 Lenalidomide Hematologic Toxicities

CTCAE 4.0 Category	CTCAE Grade	Lenalidomide Dose Modification
Absolute Neutrophil Count (ANC)¹	Grade 1 or Grade 2	Continue to treat- Do NOT OMIT and DO NOT REDUCE therapy
	Grade 3	Hold dose Administer Filgrastim Resume at same dose when ANC is \geq 1000 if neutropenia is the only hematologic toxicity If other hematologic toxicity \geq Grade 2 is present, reduce dose one level when ANC \geq 1000
	Grade 4	Hold dose Administer Filgrastim Resume therapy at one dose level lower when ANC is \geq 1000
Neutropenia with Fever ANC <1000 and temperature \geq 38.5° C or 101°F	Grade 3 or Grade 4	Hold dose Administer Filgrastim Reduce dose one level when ANC \geq 1000

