Thrombocytopenia	Grade 1 or Grade 2	Continue to treat- Do NOT OMIT and DO NOT REDUCE therapy

CONFIDENTIAL

This document is confidential. Do not disclose or use except as authorized.

Aspirin prophylaxis should be held if platelets are $\leq 50,000$	Grade 3 or Grade 4	
Provide platelet transfusion support Redraw platelets
 
If redrawn platelet value $\geq 50,000$ -> Do NOT OMIT and DO NOT REDUCE therapy
 
If redrawn platelet value $< 50,000$ continue to transfuse at the discretion of the investigator and hold therapy until platelets are $\geq 50,000$ on Day 1 or $\geq 30,000$ intracycle
 
Resume therapy at one dose level lower when the patient's platelets are $\geq 50,000$ on Day 1 or $\geq 30,000$ intracycle

	Grade 1 Grade 2 Grade 3	
Continue to treat- Do NOT OMIT and DO NOT REDUCE therapy Transfuse at the discretion of treating investigator

Anemia	Grade 4	
Hold treatment Transfuse Resume treatment when hemoglobin ≥ 8.0 g/dL DO NOT REDUCE therapy

¹ ANC can be calculated two ways: From the percentage of neutrophils: White Blood Count (WBC) x total neutrophils (polys% + bands%) x 10. From the absolute number of cells: (Absolute polys + Absolute bands) x 10.

Table 13 Lenalidomide Non Hematologic Toxicities

CTCAE 4.0 Category	CTCAE Grade	Lenalidomide Dose Modification
Infection or Viral Illness with ANC¹ ≥ 1000 Including herpes zoster reactivation	N/A	
Day 1 of Cycle: Delay cycle until infection/viral illness has resolved. Resume treatment at the same dose level. Do not dose reduce.
 
Intracycle: Hold lenalidomide for a maximum of 21 days to allow for recovery. Resume treatment at same dose level.
 
If patient has delay of greater than 21 days, the patient must come off-study

CONFIDENTIAL

This document is confidential. Do not disclose or use except as authorized.

Infection or Viral Illness with ANC¹ < 1000	N/A	
Day 1 of Cycle: Delay cycle until infection/viral illness has resolved. Administer filgrastim or equivalent as indicated.
 
Reduce one dose level when infection/virus has resolved, and ANC \geq1000
 
Intracycle: Hold lenalidomide for a maximum of 21 days. Reduce one dose level when infection/virus has resolved and ANC \geq 500
 
If patient has a delay of less than or equal to 21 days, dose reduce to next dose level. If patient has delay of greater than 21 days, the patient must come off-study

--	------------	---

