10. STUDY CALENDAR

Screening evaluations are to be conducted within 28 days of registration. Imaging assessments that are completed within 6 weeks of registration need not be repeated at screening. If a patient had a bone marrow core biopsy done within 6 weeks of registration, a bone marrow aspirate sample need only be collected for baseline and research purposes. Baseline assessments are to be conducted on C1D1 of initial therapy and should be considered separate from screening evaluations. If screening assessments are performed within 7 days of C1D1, disease assessments (SPEP, UPEP, Immunofixation, Free light chain assay, quantitative immunoglobulins) do not need to be repeated. Lab values that are used to prove eligibility for patients with progressive (evolving) smoldering myeloma do not need to be within the 21 day window, but screening values will need to be established in window. All assessments must be performed prior to administration of any study medication. See below for detailed scheduled of assessments. Study medications will be administered according to the schedule and guidelines outlined in Section 5.

	Pre-registration		Cycles 1-12 (28 days) ³				Follow-Up
Tests and procedures	≤ 28 days prior to registration	≤ 21 days prior to registration	Day 1 of cycles 1-6 ¹	Day 1 of cycles 7-12	Cycle 7 Day 1 and to confirm CR ⁸	End of Treatment ¹⁸	Every 3 Months ¹¹
History and exam, height, weight. Performance Status	X		X	X		X	X
Response Assessment ¹⁷			X	X		X	X
Toxicity Notation			X	X		X	
Hematology group (WBC w/ diff, PLT, Hgb, ANC)		X	X	X		X	X
Chemistry ⁴		X	X	X		X	X
Direct & total bilirubin ²		X	X	X		X	
Free light chain assay		X	X	X		X	X
Serum and Urine Immunofixation (SPEP and UPEP) with quantitative immunoglobulins ⁹		X	X	X		X	X
β2M, CRP, LDH ¹⁶		X	X	X		X	
TSH, Free T4, Free T3		X	X	X		X	
Metastatic Bone Survey and Spine MRI OR PET/CT only ¹⁰	X					X	
EKG ¹⁵		X				X	
Serum pregnancy test ¹²		X					
Unilateral bone marrow aspirate and biopsy ⁵	X				X	X	
Research bone marrow aspirate ⁶	X ⁵				X ⁶	X ⁶	
Research Blood ⁷	X ⁷		X ⁷	X ⁷	X ⁷	X ⁷	
Buccal Swab ¹³	X						

1- Cycle 1, Day 1 laboratory values need to meet eligibility criteria

2- Direct bilirubin to be obtained if total bilirubin is abnormal.

3- Scheduling allows for +/- 7 days all cycles.

4- Chemistry includes sodium, potassium, chloride, bicarbonate, bun, creatinine, calcium, glucose, albumin, ALT (SGPT), total protein, AST (SGOT), total bilirubin, magnesium, and phosphorus.

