Study Drug Administration	
Agent Administration Guidelines are found in Section 5.2
 
 • Nivolumab is given IV every other week on Days 1&15; Lenalidomide is PO Days 1-21; Dexamethasone is PO Days 1, 8, 15 for Cycles 1-6 ONLY • Nivolumab is given IV over 60 minutes (+/- 10 minutes); No standard premeds required, unless history of infusion reaction. A 60 min post-infusion observation period is suggested, especially during first 2 cycles, but not mandatory per protocol. • The drugs may be administered in any order. • Criteria to treat DAY 1: ANC\geq1,000; PLT\geq50; Other drug related, non-heme tox \leqGrade 1 or baseline. • Criteria to treat DAY 15: For Lenalidomide: ANC\geq1,000; PLT\geq30; Hgb\geq8 Other drug related less than Grade 3 or baseline. For Nivolumab: AST\leq90; ALT\leq156; Bilirubin\leq1.8; Creatinine\leq1.95 or \leq1.5 x baseline • Fasting is not required. • Lenalidomide capsules and Dexamethasone tablets should be swallowed whole, and should not be broken, chewed or opened. Administration should be at approximately the same time each day. If a dose is missed and less than 12 hours has elapsed since the missed dose, the patient may take the dose for that day. If more than 12 hours has elapsed since missing a dose at the normal time, the patient should not take the dose, but take the next dose at the normal time on the following day. If a dose is missed, it should be taken as soon as possible on the same day. If a dose is vomited, the dose should not be made up and the participant should continue with the regular schedule of the drug at the next dose.
Dose Mods & Toxicity	
Dose Modifications/Dosing Delay for Toxicity are outlined in Section
 
 • This protocol uses NCI CTCAE criteria, version 4.03 • There are no dose modifications for Nivolumab, there are dose reductions per protocol for Lenalidomide and Dexamethasone.
Con Meds	
Concomitant Therapy Guidelines are in Section 5.3.1
 
 • Stem cell mobilization and collection may be performed at time of best response or after 6 cycles of therapy. • Filgrastim is allowed, pegfilgrastim is NOT. • Transfusions and supportive care are allowed; bisphosphonate therapy included.

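### The second ANC formula in Table 12 footnote 1 is wrong in either usual unit: ten times too high from cells/µL, 100 times too low from 10³/µL

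*Combined protocol and SAP*

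**What the plan says.** Footnote 1 in Section 6.3 presents two routes to the ANC as alternatives. The first multiplies WBC by the summed percentages of polys and bands and then by 10. The second is "From the absolute number of cells: (Absolute polys + Absolute bands) x 10". Neither route names a unit.

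Mark 1 is attached to three rows that govern lenalidomide:

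- **Table 12, ANC row.** Grade 3 and Grade 4 lead to a hold and filgrastim. Restart requires an ANC of at least 1,000; for Grade 4 the instruction begins "Resume therapy at one dose level lower when ANC is".
- **Table 13, infection with ANC of 1,000 or more.** Lenalidomide is held for the infection and resumed at the same dose.
- **Table 13, infection with ANC below 1,000.** The dose drops one level. The intracycle instruction is "Hold lenalidomide for a maximum of 21 days. Reduce one dose level when infection/virus has resolved and ANC" at least 500. On Day 1, growth factor support is worded "Administer filgrastim or equivalent as indicated".

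The neutropenia-with-fever row of Table 12 carries no mark. It requires a hold, filgrastim and a one-level reduction.

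Two other places set ANC limits without the formula. Section 6.1 introduces its list with "For a new cycle of treatment with lenalidomide to begin, the patient must meet the following criteria" and requires at least 1,000/µL. The Special Nursing Considerations page repeats 1,000 for Day 1 and also applies it mid-cycle: "Criteria to treat DAY 15: For Lenalidomide: ANC" of at least 1,000.

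**The concern.** A sum of absolute counts needs no percentage conversion, so a factor of 10 has no role in the second formula. The two formulas are offered as interchangeable, yet they cannot agree on the same blood sample.

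The direction of the error matters. With counts in cells/µL, the formula makes a neutropenic patient look fit to dose. In the marked rows, that could mean a missed hold, an early restart or a dose reduction that is not made. With counts in 10³/µL it does the opposite and suggests holding the drug from almost everyone.

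**Working it through.** **Inputs.** The limits are 1,000/µL for eligibility (Section 3.1.4) and to start a lenalidomide cycle (Section 6.1), 1,000 to resume in Table 12, and 500 for intracycle restart in the lower Table 13 infection row. The multiplier is 10 in both formulas (footnote 1). The sample below is illustrative: WBC 2.0 × 10³/µL with 35% polys plus bands, that is 600 + 100 cells/µL.

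**Formula 1.** With WBC = W in 10³/µL and P a whole-number percentage, ANC = W × 1,000 × P/100 = W × P × 10. The printed factor is therefore reproduced: 2.0 × 35 × 10 = 700/µL. It holds only in those units. With WBC in cells/µL, the unit of the WBC limit in Section 3.1.4, it would give 2,000 × 35 × 10 = 700,000.

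**Formula 2.** The printed factor is not reproduced in either usual unit.

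| Counts entered as | Correct multiplier | Correct result | As printed (× 10) | Error |
|---|---|---|---|---|
| cells/µL: 600 + 100 | 1 | 700 | 7,000 | 10 times too high |
| 10³/µL: 0.6 + 0.1 | 1,000 | 700 | 7 | 100 times too low |

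**False passes with cells/µL.**

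- Limit 1,000: 10 × ANC ≥ 1,000 with ANC < 1,000 gives a true ANC of 100 to 999, which reads as 1,000 to 9,990.
- Limit 500: 10 × ANC ≥ 500 with ANC < 500 gives a true ANC of 50 to 499, which reads as 500 to 4,990.

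**What each marked row would do.** The documents do not print the CTCAE neutrophil cut-offs. I assume that Grade 3 begins below 1,000, the Table 12 restart limit.

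- *Table 12 ANC row.* If a site also grades with formula 2, the hold and the filgrastim are missed at a true ANC of 100 to 999. If it grades with the laboratory ANC and uses formula 2 only for restart, the hold can end early.
- *Table 13, choice of row.* An infected patient with a true ANC of 100 to 999 is placed in the upper row and restarts without the one-level reduction. The exception is a febrile patient for whom the unmarked Table 12 fever row is applied with the laboratory ANC; that row still requires the reduction.
- *Table 13, limit of 500.* This limit exists only in the lower row. It can be falsely met only if the patient was first placed there. That requires a true ANC below 100 at onset, so that formula 2 also reads below 1,000, or classification by laboratory ANC with formula 2 used only for restart.

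**When the error shows itself.** The result exceeds the total white count when 10 × ANC > WBC, that is when neutrophils are more than 10% of white cells. False passes of 1,000 that still look possible need 100 ≤ ANC ≤ WBC/10: 100 to 200 at WBC 2,000/µL and 100 to 300 at WBC 3,000/µL. In the sample above, 7,000 against a WBC of 2,000 is plainly impossible. With counts in 10³/µL, a true 3,000/µL reads as 3.0 × 10 = 30, which is equally obvious.

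**The case against.** The strongest reply is that nobody needs this formula. The footnote is permissive, and the study calendar already lists the count: "Hematology group (WBC w/ diff, PLT, Hgb, ANC". Section 6.3 adds that "The treating investigator should determine the clinical significance of laboratory values and attribution to study medications before a treatment decision is made". The correct value in cells/µL is the sum seen before multiplying. The limits in Section 6.1 and on the nursing page stand apart from the footnote, and most wrong results are visibly absurd. Filgrastim in the lower infection row is given only as indicated on Day 1, so a change of row loses no mandatory growth factor there.

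Most of this stands, and it keeps the point minor. It does not make the formula right. The separate limits cover cycle start and Day 15, but not a restart on another day. They also do not choose the Table 13 row, so they do not restore a missed reduction. The false passes that still look possible at WBC 2,000 to 3,000/µL are the most severely neutropenic ones.

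A second reply is that an exponent may have been lost from × 10³ when the text was extracted. That cannot be fully excluded, but other superscripts, such as mm³ and the footnote marks, survive. Even with 10³ the units would be unstated, and counts in cells/µL would give 1,000 times the true value.

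A reader might infer that patients were misdosed, or that the whole 100 to 999 range would go unnoticed. The documents support neither: they show no use of formula 2, and the comparison with total WBC exposes most of that range. A reader might also add the missed reduction and the false pass of 500 together. For a site using formula 2 throughout, a patient with a true ANC of 100 to 499 at onset goes to the upper row and never meets the 500 limit.

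**Conclusion.** The second formula is wrong as printed, and no other section corrects it. The error is a factor of 10 upward from cells/µL or 100 downward from 10³/µL. The unsafe direction arises only with cells/µL, and only if a site relies on the formula in the marked rows. The consequences in Table 12 rest on the assumed Grade 3 cut-off of 1,000; those in Table 13 rest on the row and restart conditions set out in the working.

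Practical exposure is small, but it cannot be given as a number of days. Section 5.1 lets participants continue lenalidomide after the September 2017 hold without stating a cycle limit there, and Section 6.1 allows delays. No endpoint, analysis or sample size depends on the footnote. Severity: minor.

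**What to change.** Correct footnote 1 so that the second route is the sum of absolute polys and bands, used unchanged when counts are in cells/µL and multiplied by 1,000 when they are in 10³/µL. State that the first route takes WBC in 10³/µL and percentages as whole numbers. Leave every ANC limit as it is, and tell sites of the correction.

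The cost is one footnote in the next amendment and a short notice. Past dosing decisions need review only at a site that reports having used the second formula.

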1.3 Duration of Study

A treatment cycle is defined as 28 consecutive days.

Patients will receive 6 cycles of induction therapy followed by 6 cycles of maintenance therapy with lower doses of lenalidomide and no dexamethasone for a total of 12 months.

During maintenance, if a patient experiences biochemical progression ($\geq 25\%$ increase and an absolute increase of $\geq 0.5\text{g/dL}$ from their nadir in their serum or urine m-spike or FLC with no CRAB features attributable to MM progression) high-dose dexamethasone may be re-added to the combination at a dose of 40mg oral given on days 1, 8, and 15 of a 28 day cycle after discussion with the overall PI.

For all treatment cycles a $+\text{-} 7$ day window is allowed for Nivolumab. For hold and delay guidelines for lenalidomide and dexamethasone, please refer to Table 17. The treatment plan is designed to be administered on an outpatient basis, however if necessary, may be given as inpatient.

Patients will be followed for up to three years after discontinuation of therapy.

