5.6 Duration of Follow Up

Participants will be followed for **3 years** after removal from protocol therapy or until progression to active symptomatic MM or need for new therapy, whichever occurs first. Participants removed from protocol therapy for unacceptable adverse event(s) will be followed until resolution or stabilization of the adverse event.

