5- A bone marrow biopsy is required within 6 weeks of registration. A bone marrow aspirate for clinical and research purposes is required pre-treatment and may be performed up to 28 days prior to registration. Both core and aspirate are required any time during the course of the study to confirm CR, and is also required at C7D1

6- Research bone marrow aspirate and biopsy at the same time as clinically indicated bone marrow biopsy and to confirm response.

CONFIDENTIAL

This document is confidential. Do not disclose or use except as authorized.

Local Protocol #: 16-242

Version Date: 23 January 2018

7- Peripheral blood samples for correlative studies may be done at any time pre-treatment, though baseline and C1D1 samples should be considered separate time points.

8-If C7D1 or confirmation of response BM aspirate and core biopsy was performed within 3 weeks of either timepoint, the procedure need not be repeated. At minimum, an aspirate sample is required

9- Disease assessment/response assessment is required each Day 1 starting with C2-If the participant's disease response is not followed primarily via a UPEP (24 hour urine collection) and Urine immunofixation, these tests may be done only at screening, end of treatment, and every 3 months during treatment.

10-A CD of scans at screening and end of treatment is required to be sent to the lead site for central review. Screening scans should be sent with the eligibility packet to the lead site- This requirement includes a full body skeletal survey in addition to spinal MRI OR the patient may have only a low dose PET CT

11- Follow-up should occur every 3 months (+/- 14 days) for up to 3 years after end of treatment.

12- Women of child-bearing potential must abide by revlimid REMS procedures and may require additional pregnancy testing as described in section 3.1.7.

13- Buccal swab may be collected at any time throughout the study but should be collected pre treatment on C1D1

14- Thyroid labs are required at screening, C3D1, C6D1 and every 3 cycles thereafter, at end of treatment, and at any time that it is clinically indicated

15- Alert Overall PI immediately if there is concern for cardiac toxicity (At minimum, the following should be performed: cardiology consult, EKG, echocardiogram, and labs CPK and troponin; refer to section 6.2.7 for more details)

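### Three Table 13 rows take a patient off study after a lenalidomide-related delay over 21 days, although 6.1 only stops treatment and 5.6 continues follow-up; read literally, the 2-year status goes unobserved

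*Combined protocol and SAP*

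**What the plan says.** In Table 13 of section 6.3, three rows end with the sentence "If patient has delay of greater than 21 days, the patient must come off-study". They are infection or viral illness with ANC at or above 1000, infection or viral illness with ANC below 1000, and Grade 4 events among the other related toxicities. The table's scope is set just before it: "For adverse non hematologic events that are considered to be possibly, probably or definitely related to Lenalidomide". The same sentence goes on to allow departures: "the following criteria for retreatment and dose modification should be followed unless discussed and approved first by the overall principal investigator".

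Other sections treat the same situation differently:

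- Section 6.1: "The maximum delay for toxicity related to study treatment before treatment is permanently discontinued will be 3 weeks". If a longer delay is clinically necessary "and the patient is showing benefit from treatment, the patient may continue on study after discussion and approval by the Principal Investigator".
- Section 5.6: participants are followed for 3 years "after removal from protocol therapy or until progression to active symptomatic MM or need for new therapy, whichever occurs first". A second sentence says that those removed for unacceptable adverse events are followed until the event resolves or stabilises.
- Section 1.3: "Patients will be followed for up to three years after discontinuation of therapy".
- Section 10, calendar note 11: "Follow-up should occur every 3 months (+/- 14 days) for up to 3 years after end of treatment". Note 17 requires a response assessment at each of those visits.
- The note under Table 13: a patient who stops lenalidomide need not leave protocol therapy.
- Section 5.7: the off-study reasons are loss to follow-up, withdrawal of consent for data submission, death, and progression with subsequent treatment. Dose delay is not listed.

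**The concern.** The protocol separates leaving therapy (5.5) from leaving the study (5.7), and elsewhere it uses the therapy term correctly, for example for confirmed myocarditis in 6.2.7 and in the note at the end of Table 11. A site that reads a mandatory off-study instruction in a dosing table could therefore apply the 5.7 meaning and stop assessing the patient.

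The primary endpoint is progression-free status at 2 years, and 13.1.1 keeps every treated patient in the analysis. A patient removed this way would be in the denominator with no observed 2-year status, and the reason for the gap, a prolonged toxicity-related delay, may be related to outcome. The rule is also uneven. The Table 13 rows for allergy, renal or metabolic toxicity, and gastrointestinal toxicity carry no such consequence, so a 22-day hold for infection would end follow-up while a 22-day hold for Grade 4 diarrhoea would not.

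The rows remain live after the September 2017 partial hold, because sections 1.1 and 5.1 let patients stay on lenalidomide. Accrual is closed, so lost outcomes cannot be replaced.

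**Working it through.** **The texts side by side.** Table 13 and 6.1 share one threshold (21 days, 3 weeks) but attach different consequences: off study in the table, treatment stopped in 6.1. Sections 5.6 and 1.3 and calendar note 11 make no exception for toxicity delays in the follow-up after therapy. The note under Table 13 goes further than 6.1, because stopping lenalidomide need not end protocol therapy at all. These conflicts are firm. Two are softer: the 5.7 list is not stated to be exhaustive, and note 17 names withdrawal as an end of assessment without defining it.

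**Timing of a literal removal.** Inputs: 28-day cycles, 12 cycles, lenalidomide on days 1 to 21 (sections 1.3 and 5.1), three-monthly follow-up (note 11). Conventions: landmark at day 730; the limit is exceeded 22 days after the delay starts; one interval is 91.3 days.

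1. Planned end of treatment: 12 × 28 = day 336.
2. Earliest case, lenalidomide held from day 2: 2 + 22 = day 24. Gap: 730 − 24 = 706 days; 706 / 91.3 = 7.7 intervals.
3. Late case, Cycle 12 Day 1 delayed: that day is 11 × 28 + 1 = 309, and 309 + 22 = day 331. Gap: 730 − 331 = 399 days; 399 / 91.3 = 4.4 intervals.
4. Outer bound, end of planned treatment: 730 − 336 = 394 days; 394 / 91.3 = 4.3 intervals.
5. Off schedule, with a 21-day delay in every cycle: 336 + 12 × 21 = day 588, still 730 − 588 = 142 days before the landmark.

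On schedule, then, about 7 to 4 three-monthly assessments would be missed. Earlier permitted delays shorten the gap; longer delays approved by the principal investigator could shorten it further.

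**The design figures.** Section 13.1 requires at least 24 of 39 progression free, with stated alpha 0.10 at a 50% rate and power above 0.9 at 70%. Exact binomial: P(X ≥ 24 | 39, 0.5) = 0.0998 and P(X ≥ 24 | 39, 0.7) = 0.9056. Both reproduce.

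**Sensitivity, on assumed inputs only.** The documents give no rate of qualifying delays, and 13.1.1 does not say how an unobserved status counts.

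- Suppose a share q is removed independently of progression and counted as failures. Power at 70% is P(X ≥ 24 | 39, 0.7(1 − q)): 0.858 for q = 2.5%, 0.797 for 5%, 0.643 for 10%, 0.466 for 15%.
- Suppose instead that k removed patients are counted as progression free. Type I error is P(X ≥ 24 − k | 39 − k, 0.5): 0.128 for k = 1, 0.162 for k = 2, 0.250 for k = 4.

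These show how a 39-patient rule responds to a few unobserved outcomes. They do not estimate what happens in this trial.

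**The case against.** The strongest defence is that off-study here simply means off treatment. Sections 5.5 and 5.7 use one combined Treatment Ended/Off Study Form on removal from protocol therapy, 6.1 attaches a treatment consequence to the same limit, and the follow-up provisions are plain. A site reading the whole protocol would probably keep assessing the patient. This stands, and it makes the harm conditional.

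Next, there are ways out. Section 6.3 allows departures with approval, 6.1 allows longer delays, and 1.1, 6.1 and 6.2 let a patient remain on study after a drug is permanently stopped. This stands in part. All of these depend on the principal investigator's approval or discretion, so the default instruction in the three rows is still removal.

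Third, the adverse-event sentence in 5.6 could be read as the whole follow-up rule for toxicity removals. I read it as additional, since 1.3 and note 11 contain no such carve-out, but the text does not say so. A correction that only pointed to 5.6 would inherit that ambiguity.

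A reader might also stretch the removal window to day 351, taking a hold from the last scheduled lenalidomide dose (11 × 28 + 21 = day 329) plus 22 days. The documents do not support this: 6.3 says held doses are missed and not made up, so no later dose is left to delay, and planned treatment ends on day 336.

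**Conclusion.** The inconsistency is real and should be corrected. Three operative rows, taken literally, end progression assessment before the primary time point, contrary to 6.1, 5.6, 1.3, calendar note 11 and the note under the table. For an affected patient treated on schedule, removal falls between about day 24 and about day 331, and no later than day 336, which is roughly 706 to 394 days short of day 730.

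The size for the trial is unknown and probably small. Only patients with a lenalidomide-related delay over 21 days, no approved exception and a site that applies the wording literally would be affected.

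A reader might infer that the plan in fact abandons follow-up of these patients, or that the trial is underpowered. The documents support neither. The surrounding text points to loose wording, no rate of such delays is given, and the stated alpha and power reproduce. No stated alpha, power or sample size is wrong because of this point. The timing rests on the 12-cycle plan and a 730-day landmark.

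**What to change.** In each of the three Table 13 rows, replace the off-study clause with: 'lenalidomide must be permanently discontinued unless the overall PI approves a longer delay (6.1, 6.3); whether or not other protocol therapy continues, the patient stays in follow-up with the scheduled 3-monthly progression assessments (calendar notes 11 and 17) until progression, new therapy, death, withdrawal of consent or 3 years'.

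In 5.6, add that following an adverse event to resolution or stabilisation is in addition to the 3-year progression follow-up and does not replace it.

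The cost is wording in three table rows and one sentence in 5.6. The visits are already scheduled, so no procedure, sample size or analysis changes.
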